### 4.2.2.2 Evaluation of Response

Appropriate imaging with CT of the chest/abdomen/pelvis and MRI (if target lesion is best visualized by MRI) to reassess tumor extent and to determine tumor measurements will be performed 14 weeks after completion of radiotherapy and with each subsequent dose of vaccine thereafter (with windows for treatment as designated in the schedule of events, [Section 1.5](#)).

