## 4.2.3 After Treatment Completion

Post-treatment follow-up will be conducted 30 (+/- 2) days after last dose of treatment. The visit should include a history and physical exam; labs with CBC/differential and serum chemistries; assessment of trial drug AEs; RECIST 1.1 assessment; and CT chest, abdomen, and pelvis, and MRI (if target lesion is best visualized by MRI). If patient had abnormal physical exam findings or abnormal lab values at the off-treatment time point, then the patient should have follow-up visit with the primary oncologist to focus on the abnormal finding(s). Results and report findings should be faxed or emailed to the trial team.

Once the 30 day follow up assessment is completed, the patient is then taken off trial.

Patients removed from trial for any reason must be followed for at least 30 days after the last dose of vaccine or until all toxicities have resolved to baseline or stabilized, whichever is later.

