#### 4.2.6 Premature Discontinuation

Patients will discontinue the trial if any of the following are true:

- Participant requests to be withdrawn from trial; in this event, the reasons for withdrawal will be documented. If at all possible, the patient should return for the Post Treatment Follow-up Visit.
- A patient who is noncompliant with protocol guidelines may be removed from the trial at the discretion of the principal investigator.
- Disease progression, as described in Removal from Protocol Therapy [Section 4.2.5](#)
- Death.

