Standard RECIST 1.1 evaluations based on all lesions will be performed by external radiological reviewers and results will be included in exploratory analyses.

Each patient will be assigned one of the following categories: 1) CR; 2) PR; 3) SD; 4) progressive disease; and 5) not evaluable (death prior to restaging from malignant disease, toxicity, or due to other causes; or insufficient data). Patients will be assessed at fixed intervals as indicated by the schedule of events ([Section 1.5](#)).

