**BRACHY-CHOR-001** 

- Completed radiation therapy, and
- At least 3 out of 4 booster doses of FPV-Brachyury in 14 weeks after radiation, and
- Have both baseline (defined as measurement prior to first prime dose of MVA-BN-Brachyury), and at least one post-baseline computed tomography (CT) or magnetic resonance imaging (MRI) scan for objective tumor evaluation.

The primary analysis population for ORR anytime within 12 months after completion of radiation and secondary efficacy endpoints is the EAS. Subjects who failed to meet the evaluable criteria will be replaced to retain the statistical power unless four or more responses have been observed or the number of responders will still be less than four even if all replacement subjects would be responders. If there are more than 10 evaluable subjects at the end of stage 1 analysis or more than 29 evaluable subjects at the end of stage 2 analysis, primary evaluation will be based on the first 10 accrued or first 29 accrued evaluable subjects. Sensitivity analyses will include all evaluable subjects if applicable.

The FAS consists of all subjects who have enrolled and received any dose of MVA-BN-Brachyury or FPV-Brachyury. This is the primary analysis set for safety and immune response, and the secondary analysis set for efficacy.

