## 3.4.2 Data Handling Conventions for Efficacy Analyses

For PFS, if a subject has no date of death and has not progressed by the time of the analysis, the subject will be censored at the last radiologic assessment showing that no progression has occurred.

Subjects who have no record of CR/PR and withdraw early from the trial or are lost to follow-up will be considered as non-responders for the ORR analyses and will be considered to have progression for the by-time-point PFS analyses.

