## 3.5.3.2 Response Criteria

### **Primary and Secondary Endpoints**

mRECIST criteria will be used for radiographic assessment of the irradiated tumor(s) (target lesions) only. Non-irradiated tumors (non-target lesions) will not be assessed for the primary endpoint by mRECIST, but clinical decisions based on tumor growth may be made on investigator discretion. Additionally, at investigator discretion, irRC principles can be used for target lesion(s). If a subject has enlargement of their target lesion(s) at the first restaging scan after completion of radiotherapy, they may remain on trial until confirmation of progression on a subsequent scan (at least 4 weeks later). Similarly, any response must also be confirmed with a repeat scan at least 4 weeks later. Progression of a non-target lesion does not result in disease progression by the mRECIST evaluation to be used in this trial. The purpose of the trial is to determine if radiation plus vaccine can shrink the irradiated tumor. In these cases, local interventions may be considered to other non-target lesions (surgery, radiation, or ablation) at the investigator's discretion. Progression of any non-target lesion that requires systemic treatment will result in the subject being taken off trial. If a subject must come off trial due to progression of any non-target lesion prior to meeting the evaluable definition, they may be replaced with another subject to ensure statistical power is maintained for the primary analysis.

In some cases, if more than one lesion can be irradiated, multiple target lesions may be selected. Only those that receive adequate radiotherapy (as defined by radiation requirements for enrollment in the trial protocol) will be considered target lesions for RECIST assessments and primary endpoint analysis.

BRACHY-CHOR-001

All subjects in this trial must be assessed for response to treatment, even if there are major treatment deviations. If a subject has not completed adequate treatment to be evaluated for response to treatment, they should still be assessed, but may be replaced to maintain statistical power. The primary endpoint assessment of ORR anytime within 12 months following completion of radiation will be based on the response to adequate treatment, which will require vaccination and completion of adequate radiotherapy. Progression prior to that point will not be considered treatment failure for purposes of primary endpoint analysis.

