## 3.5.3.4 Secondary Efficacy Analyses

## 3.5.3.4.1 PFS Based on Target Lesion(s)

PFS is defined as the time interval from first vaccination to objective tumor progression based on the mRECIST criteria or death, whichever occurs first. Subjects who do not have disease progression or have not died will be censored at the date when the last tumor assessment determines a lack of target tumor progression. The product-limit Kaplan-Meier curve will summarize PFS graphically. Median survival and 95% confidence intervals will be computed based on the product limit method (Greenwood's formula for the standard error estimate) overall and by subgroups defined in Section 3.3. Progression-free survival rates will be summarized by visit where scheduled tumor assessment is performed, along with their Wilson score confidence intervals.

Primary analyses of PFS will be based on the EAS. PFS rates will also be summarized for the FAS where subjects without post-treatment tumor assessment will be considered to have progressed. Median survival and 95% confidence interval will not be analyzed for the FAS, as these estimates will not differ from those for the EAS because censoring at time 0 is equivalent to excluding these subjects.

Additionally, PFS from current treatment versus PFS from previous treatment will be explored. The ratio of current treatment PFS in days / previous treatment PFS in days for each subject will be calculated. Summary statistics will be presented for EAS. It will also be summarized for EAS by current radiation treatment dose categories: <= median current radiation dose in Gray and > median current radiation dose in Gray. Highest dose of radiation treatment for each subject is used as defining the current radiation treatment dose categories. Subject's most recent previous treatment will be used for the derivation and calculation of PFS from previous treatment. Figures will also be generated to present the ratio by overall and by current treatment radiation dose categories.

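### The SAP drops the FAS median PFS because it would equal the EAS median, but its own event and censoring rules do not assure this

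*SAP*

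**What the plan says.** SAP 3.5.3.4.1 makes the EAS the primary set for PFS. For the FAS it keeps PFS rates by visit, counting subjects with no post-treatment scan as progressed. It omits the FAS median and 95% CI, "as these estimates will not differ from those for the EAS because censoring at time 0 is equivalent to excluding these subjects".

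The rules that decide whether this is so are elsewhere:

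- **PFS event.** The SAP's General Definitions and 3.5.3.4.1 count progression or death, whichever comes first. Death from any cause qualifies.
- **Censoring.** SAP 3.4.2: "if a subject has no date of death and has not progressed by the time of the analysis, the subject will be censored". The censoring date is the last radiologic assessment without progression.
- **EAS membership.** SAP 3.2 requires both prime doses, the pre-radiation booster, completed radiation, "At least 3 out of 4 booster doses of FPV-Brachyury in 14 weeks after radiation, and" a baseline and at least one post-baseline scan. The FAS needs only one vaccine dose.
- **First scan.** Protocol 4.2.2.2: imaging "will be performed 14 weeks after completion of radiotherapy and with each subsequent dose of vaccine thereafter".
- **Subjects outside the EAS.** SAP 3.5.3.2: "All subjects in this trial must be assessed for response to treatment, even if there are major treatment deviations".

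Protocol 10.4.5.2 says the secondary endpoints are also analysed on the FAS. SAP Section 4 lists two other changes from plan, not this one.

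**The concern.** The SAP's reason treats every FAS subject outside the EAS as censored at time 0. Only one of the five EAS criteria concerns scans; the other four concern treatment. A subject can therefore be outside the EAS and still have a PFS event or a positive censoring time.

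If the sentence stands, the only median PFS reported comes from subjects who lived to receive a third post-radiation booster and had a scan. The SAP would also assure readers that this is the FAS median. In a single-arm trial, where PFS is read against outside experience, that assurance should be correct.

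**Working it through.** **1. When the SAP's statement is true.** The Kaplan-Meier factor at each event time is 1 − d/n, where n is the number still at risk. A subject censored at time 0 is in no risk set and causes no event, so every factor is unchanged. The median and CI are then identical. The statement is correct for living FAS subjects who were never scanned, and also harmless for anyone censored before the first EAS event.

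**2. Route one: death before any scan.** Radiation starts on Day 42 to 56 (Day 28 booster plus 2 to 4 weeks). It lasts from 1 day to about 60 days: (50.4 + 27)/1.8 = 43 fractions, assuming five a week. The first scan follows 98 days later:

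- earliest: (42 + 1 + 98)/7 = week 20
- latest: (56 + 60 + 98)/7 = week 31

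A death in that window has a death date, so SAP 3.4.2 does not censor it; it is an event. With no post-baseline scan it cannot be in the EAS. Protocol 10.5 foresees the case in its category "not evaluable (death prior to restaging from malignant disease, toxicity, or due to other causes; or insufficient data".

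**3. Route two: scanned subjects who missed doses.** An adequately irradiated subject with fewer than three of the four boosters is outside the EAS but must be assessed. Protocol 4.2.3 puts "RECIST 1.1 assessment; and CT chest, abdomen, and pelvis, and MRI" in the post-treatment visit, and Protocol 4.2.6 says of subjects who withdraw: "If at all possible, the patient should return for the Post Treatment Follow-up Visit". Protocol 4.2.5 keeps those stopped for toxicity in follow-up until progression. There are limits: a subject without adequate radiation has no target lesion (SAP General Definitions), and one who leaves after the 30-day visit may be censored too early to matter.

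**4. Direction and size by rank.** Take 29 EAS subjects, none censored before the median, and use the midpoint when the curve equals 0.5 exactly.

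- EAS alone: after 14 events S = 15/29 = 0.517; after 15, S = 14/29 = 0.483. The median is the 15th event time.
- Add one pre-scan death: after it and 14 EAS events, S = 15/30 = 0.5. The median is midway between the 14th and 15th EAS event times, so it is **shorter** by half that gap.
- Add instead one dose-misser progression-free to the last scan: after 15 events S = 15/30 = 0.5. The median is midway between the 15th and 16th, so it is **longer**.
- Add both: after the death and 14 EAS events S = 16/31 = 0.516; after 15, S = 15/31 = 0.484. The median is the 15th event time again; the effects **cancel**.

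**5. Size in weeks.** The documents give no PFS data and no count of FAS-only subjects, so this is an illustration: 29 EAS subjects, exponential PFS with median 39, 52 or 78 weeks, nine scans 12 weeks apart, events dated to the next scan.

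| Added to the EAS | Effect on median |
|---|---|
| Living, never scanned | none in any trial |
| One pre-scan death, all subjects on one scan grid | usually 0 or 6 weeks shorter |
| One pre-scan death, first scans spread over weeks 20 to 31, ±2-week window | typically 1.3 to 2.6 weeks shorter |
| One pre-scan death, average under either scheme | about 2 to 4 weeks shorter |
| Sampling SD of the EAS median | 10 to 19 weeks |

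With spread dates, a shift of 6 weeks or more occurs in 4%, 9% and 19% of trials for medians of 39, 52 and 78 weeks.

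A separate calculation used evenly spaced quantiles and took the median as the first time S is at or below 0.5. Three pre-scan deaths moved a median of 12.0 months to 10.7, and 18.0 to 15.6. In the 12-month case one death left the log-log 95% CI at 8.5 to 16.3; three moved it to 7.6 to 15.3.

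**6. Is one death a reasonable illustration?** Assume exponential survival, so the pre-scan death probability is 1 − exp(−hL). Protocol 2.1 gives a 6- to 7-year median survival; one trial in Protocol Table 1 had 86.5% alive at 12 months.

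- Lowest: h = ln2/(7 × 52.18), L = 20 weeks, gives 3.7%.
- Highest: h = −ln(0.865)/52.18, L = 31 weeks, gives 8.3%.

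For 29 subjects that is 29 × 0.037 = 1.1 to 29 × 0.083 = 2.4 deaths, or about half as many if the exclusion of rapidly progressing multi-site disease halves the rate. Two deaths move the median to the 14th EAS event time (15/31 = 0.484), twice the one-death shift.

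**7. Can the retained FAS rates stand in?** Suppose five FAS-only subjects were never scanned. Before any EAS event the FAS rate is 29/34 = 85.3%, whether none or all of the five died. The rate does not show whether the medians differ.

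**The case against.** The strongest reply is that the plan already gives more than the omitted median would. The by-visit FAS rates count every unscanned subject as progressed, and SAP 3.4.2 adds early withdrawals without a response, so they are stricter than a FAS median. SAP 3.5.1 lists all individual and derived data, and SAP 3.5.4 lists EAS exclusions with reasons, so a reader could rebuild the FAS curve. The endpoint is descriptive, and no test or go/no-go decision uses it. Deaths after a subject leaves the trial may not be recorded; such subjects would fall back to time-0 censoring. All of this stands as mitigation. None of it reports the FAS median or makes the stated reason true.

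A reader might infer three stronger points that the documents do not support:

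- **That the EAS median flatters the product.** Early deaths would do that, but long progression-free dose-missers do the opposite, and nothing says which will occur.
- **That frequent disagreement means a large effect.** With one pre-scan death and a 52-week median, the medians differ in 37% to 38% of trials on a shared scan grid, usually by 6 weeks. With spread scan dates they differ in about 99% to 100%, but typically by only 1.3 to 2.6 weeks across medians of 39 to 78 weeks. The frequency reflects the grid and the midpoint rule.
- **That the omission breaches the protocol.** Protocol 10.4.5.2 does not name the median, the SAP does analyse PFS on the FAS through the rates, and Protocol 10.1 leaves full analysis details to the SAP.

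**Conclusion.** The reason given for omitting the FAS median PFS is wrong as written. It covers living subjects who were never scanned, not deaths before the first scan or scanned subjects excluded for missed doses. Equality is not assured, and the direction cannot be known in advance.

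The effect is probably small. One pre-scan death shifts the median by about 2 to 4 weeks on average, well inside its sampling SD of 10 to 19 weeks. This rests on 29 EAS subjects, exponential PFS with a median of 39 to 78 weeks, and 12-weekly scans. More FAS-only events of one kind would enlarge the shift; a mixture could cancel it. ORR success is unaffected. The point merits correction because the sentence is a factual assurance that the plan's own rules do not support, and the correction is cheap.

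**What to change.** In SAP 3.5.3.4.1, delete the sentence equating the two sets. Report the FAS Kaplan-Meier curve, median and 95% CI under the existing event and censoring rules, beside the EAS result and the retained FAS rates. If the FAS median is still left out, give a correct reason and note the omission in SAP Section 4.

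The cost is one extra table and one figure from data already collected. The FAS median may be less favourable than the EAS median. Living subjects with no scan still contribute nothing to it, so the by-visit FAS rates remain necessary.

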## 3.5 Analysis and Presentation Methods

#### 3.5.1 General Presentation Methods

Categorical variables will be summarized using frequencies and percentage of subjects within each category, unless otherwise stated. Continuous variables will be summarized using the following statistics: mean, standard deviation, median, minimum, and maximum. Variables that are log normally distributed will be presented using geometric means and confidence intervals. Percentages will be presented to one decimal place. If a frequency is 0, the percentage will not be presented to draw attention to the non-zero cells of the tables.

For continuous statistics, precision will be based on the precision of the original data points. Means and medians will be presented to the original precision plus one decimal place. Standard deviations will be presented to the original precision plus two decimal places. The minimum and

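### The current-to-previous PFS ratio has no rule for censored current PFS and no definition of previous PFS: censoring biases it downward, and its net direction is unknown

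*SAP*

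**What the plan says.** SAP 3.5.3.4.1 defines the current time: "PFS is defined as the time interval from first vaccination to objective tumor progression based on the mRECIST criteria or death, whichever occurs first". It then censors: "Subjects who do not have disease progression or have not died will be censored at the date when the last tumor assessment" showed no target progression. SAP 3.4.2 agrees: "the subject will be censored at the last radiologic assessment showing that no progression has occurred". For PFS itself the plan uses Kaplan-Meier.

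The ratio comes later in the same section: "The ratio of current treatment PFS in days / previous treatment PFS in days for each subject will be calculated". Its reporting rule is "Summary statistics will be presented for EAS", repeated by radiation dose group (at or below the median dose, and above it), with figures overall and by dose group. SAP 3.5.1 sets the default: "Continuous variables will be summarized using the following statistics: mean, standard deviation, median, minimum, and maximum".

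For the denominator the plan says only: "Subject's most recent previous treatment will be used for the derivation and calculation of PFS from previous treatment". For the numerator, SAP 3.5.3.2 adds: "Progression of a non-target lesion does not result in disease progression by the mRECIST evaluation to be used in this trial".

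**The concern.** A censored current PFS is a lower bound, so the ratio built on it is also a lower bound. The plan asks for a ratio for every subject and summarises the ratios with statistics that cannot tell a bound from an observed value. Nothing says whether censored ratios are flagged, dropped or used as they stand.

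The denominator is a second problem. No start date, evidence of progression or lesion set is given for previous PFS, nor any rule for subjects with no prior treatment or no prior progression. The numerator counts only irradiated target lesions.

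This is the SAP's only comparison with a subject's previous treatment, in a single-arm trial. It is also split by dose group, where unequal censoring could create or hide a difference.

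**Working it through.** **Plan's own figure.** The documents give no number for the ratio, so there is none to reproduce.

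**Inputs.**
- Previous median 9 months: an assumption. Protocol Table 1 shows median PFS of 8, 9 and 9.9 months in single-arm phase 2 trials of systemic therapy.
- Follow-up C = 28 months: an assumption within the limit of 29 months per patient in Protocol 4.3.
- Current median m = 9, 18 or 27 months, and 0% or 20% per year leaving: assumptions, shown as a range.
- Current time T and previous time P: independent and exponential.

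**Formulas.** Let μ = ln2/9, λ = ln2/m, δ = leaving rate and a = λ + δ.
- True ratio: P(T/P > r) = μ/(μ + λr), which is 1/2 at r = m/9.
- Censored times used as complete: P(observed ratio > r) = μ/(μ + ar) × [1 − exp(−(μ + ar)C/r)]. Set this to 1/2 for the median.
- Censored fraction: 1 − (λ/a)(1 − exp(−aC)). With no leaving this is 2^(−28/m).

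**Worked case, m = 18, no leaving.** μ = 0.07702 and λ = 0.03851. At r = 1.64, μ + ar = 0.14017, so 0.5495 × (1 − exp(−2.393)) = 0.5495 × 0.9086 = 0.499.

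**Worked case, m = 18, 20% per year leaving.** δ = −ln(0.8)/12 = 0.0186 and a = 0.0571. At r = 1.25, μ + ar = 0.1484, so 0.5190 × (1 − exp(−3.324)) = 0.5190 × 0.9640 = 0.500.

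| Current median | Leaving per year | Censored | True median ratio | Censored as complete | Loss |
|---|---|---|---|---|---|
| 9 | 0 | 12% | 1.00 | 0.97 | 2.5% |
| 18 | 0 | 34% | 2.00 | 1.64 | 18% |
| 27 | 0 | 49% | 3.00 | 2.00 | 33% |
| 18 | 20% | 46% | 2.00 | 1.25 | 37% |

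Simulation of the same inputs gave 0.98, 1.63, 2.01 and 1.25, in agreement to about 0.01.

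**Sensitivity to the 9 months.** Put r = kμ/λ. The expression becomes 1/(1 + ka/λ) × [1 − exp(−(λ/k + a)C)], which does not contain μ. The percentage loss is therefore the same for any previous median, including 8 or 9.9 months.

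**Other ways to fill the gap.**
- Dropping censored subjects is no better. In simulation with m = 18 the median was 1.05 with no leaving and 0.92 with 20% per year leaving, against a true value of about 2.
- Kaplan-Meier on the ratio overshoots: 2.46 against a true 1.98 (m = 18, no leaving, 27-month ceiling, previous PFS floored at 1 month). On the ratio scale the censoring point is C/P, which depends on the same P as the ratio.

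**Does a bounded share work?** Take ratio > 1 and m = 18. The true share is μ/(μ + λ) = 66.7%. The lower bound is μ/(μ + a) × (1 − exp(−(μ + a)C)), and the upper bound is 1 − λ/(μ + a) × (1 − exp(−(μ + a)C)).
- No leaving: 0.6667 × 0.9606 = 64%, and 1 − 0.3333 × 0.9606 = 68%.
- 20% per year leaving: 0.5742 × 0.9766 = 56%, and 1 − 0.2871 × 0.9766 = 72%.

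Both intervals contain the true share, and their width shows how much the censoring hides.

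**Denominator.** The prior-therapy list in SAP 3.5.6.1 has duration, best response and reason for stopping, but no progression date. SAP 3.5.5.2 uses a recurrence date after the primary curative intervention, which need not be the most recent previous treatment. Ignoring non-target progression can only lengthen current PFS or leave it unchanged, so any mismatch probably acts against the censoring bias.

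**The case against.** The strongest reply is that the ratio is only explored. It has no hypothesis, alpha, threshold or decision role. That stands, and it limits the weight of the point, but it does not make the stated calculation sound.

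It can also be said that the SAP never declares censored times complete. That is true: the reading rests on the words requiring a ratio for each subject, on the default statistics, and on silence. The table and figure shells are in a separate document (SAP Appendix 2) and might flag censored points. Derived data are listed by subject. Neither changes the summary statistics that the SAP specifies.

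The simulation inputs are assumptions. The 9-month benchmark comes from systemic therapy, whereas the last treatment may have been surgery or radiation. EAS entry (three of four post-radiation boosters and a post-baseline scan) removes some early leavers. With few subjects censored, the median hardly moves.

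A reader might infer more than the documents support:
- That the two progression definitions are shown to differ. They are not; previous PFS is undefined, so a match cannot be shown.
- That this is the only within-patient comparison. It is not; the SAP also has percent change from baseline in target lesions, BPI-SF shifts from baseline and ELISPOT ratios to baseline.

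**Conclusion.** The point holds as a defect in an exploratory analysis. As written, censored current PFS enters the ratio as if complete and biases it downward. In the cases worked, the loss in the median is about 2.5% at 12% censored, 18% at 34% and 33% at 49%. With 20% per year leaving it is 37% at 46% censored. These sizes rest on independent exponential times and 28 months of follow-up; the actual censoring fraction is not in the documents.

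A reader might conclude that the reported statistics are simply wrong, or that the ratio will understate benefit overall. Neither follows. The censoring bias can be slight, and the target-lesion-only numerator over an undefined denominator may push the other way. The net direction is unknown. The primary ORR test and the Kaplan-Meier PFS do not use the ratio and are unaffected. The change should be made, but nothing confirmatory depends on it.

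**What to change.** In SAP 3.5.3.4.1:

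1. Carry the censoring flag into the ratio. Mark censored ratios as lower bounds in tables and figures, and report their number overall and by dose group.
2. Replace the plain mean and median as the main summary with the share of subjects above a pre-stated cut-off (for example, ratio > 1). Count ratios censored below the cut-off once as failures and once as successes. Use a subject-stratified (paired) Cox model in addition or instead. Do not rely on Kaplan-Meier of the ratio alone.
3. Define previous PFS: its start, the evidence of progression, the lesions counted, and the handling of subjects with no prior treatment or no prior progression.
4. State whether the SAP 3.4.2 rule that counts certain early withdrawals as progressed, now limited to by-time-point PFS, applies to the ratio.
5. Caveat the target-lesion-only numerator. The SAP offers no all-lesion PFS to substitute, because the standard RECIST 1.1 analyses will not be performed (SAP 3.5.3.5 and Section 4).

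The cost is a few lines of SAP text and programming, and a less compact summary. The paired model handles censoring but does not cure a mismatch in definitions.
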